### 3.5.3.2 Assessment of Safety Topics of Special Interest

There are no safety topics of special interest in this study.

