2.3 Benefit/Risk Assessment

It cannot be guaranteed that participants in clinical studies will directly benefit from study participation, as clinical studies are designed to provide information about the safety and efficacy of an investigational medicine.

MK-6194 administered subcutaneously appears to be generally well tolerated in the completed and ongoing Phase 1 clinical studies at single doses [REDACTED] CCI [REDACTED]

[REDACTED]. The number of participants exposed to multiple doses of MK-6194 over several weeks is continuously increasing due to the ongoing clinical development across several indications. The most frequently reported AEs are cutaneous AEs, including injection-site reactions, and elevated absolute eosinophil count. The cutaneous AEs were generally mild or moderate in intensity, self-limited, and did not require medical therapy. Transient mild to moderate increased absolute eosinophil counts have been observed in some participants who received MK-6194, which returned to normal range or were trending toward normal by the end of the treatment. There have been no events of eosinophil-associated organ injury. Injection-site reactions and increased eosinophil counts have been previously reported in patients receiving recombinant IL-2, including low-dose IL-2, for the treatment of autoimmune diseases [Fantom, C., et al 2020] [Van Gool, F., et al 2014] [Rosenzwajg, M., et al 2019].

The benefit/risk assessment for MK-6194 is considered favorable for its evaluation as a potential treatment for the treatment of vitiligo.

Additional details are provided in the IB and informed consent documents.

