4.2.1.2 Safety Endpoints

General safety and tolerability will be evaluated by clinical review of all relevant parameters, including AEs, vital signs, and laboratory safety tests (hematology, chemistry, and urinalysis), performed per the SoA (Section 1.3). AEs will be evaluated and assessed according to the guidelines in Section 8.4. Participants may be asked to return for unscheduled visits to perform additional safety monitoring.

In MK-6194 studies, absolute eosinophil counts will be measured at baseline and monitored during treatment. Participant discontinuation criteria related to clinically significant elevated eosinophil counts and/or evidence of eosinophil-related organ injury have been implemented (Section 7.1).

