6.6.3 Management of Eosinophilia

For participants with AEC \leq 650 cells/ μ L at Screening:

- If AEC is >1000 cells/ μ L at a scheduled or unscheduled visit after Randomization, another CBC with differential must be performed before the next dose. It is recommended to perform the CBC with differential close to the next dosing day and at least 10 days after the prior dose.
- If AEC is still >1000 cells/ μ L, a CBC with differential may be repeated the day before the dosing day or on the dosing day, prior to administration of study intervention.
- If AEC remains >1000 cells/ μ L, study intervention should be interrupted. Study intervention may be restarted once AEC is ≤ 1000 cells/ μ L.

For participants with AEC >650 cells/ μ L at Screening:

- If AEC at a scheduled or unscheduled visit after Randomization has an increase of ≥ 500 cells/ μ L above the Screening value, another CBC with differential must be performed before the next dose. It is recommended to perform the CBC with differential close to the next dosing day and at least 10 days after the prior dose.
- If AEC is >1000 cells/ μ L, a CBC with differential may be repeated the day before the dosing day or on the dosing day, prior to administration of study intervention.
- If AEC remains >1000 cells/ μ L, study intervention should be interrupted. Study intervention may be restarted once AEC is ≤ 1000 cells/ μ L.

Hypereosinophilic syndrome and eosinophil-associated organ injury are described in Appendix 9.

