8.4.7 Events of Clinical Interest

Selected serious and nonserious AEs are also known as ECIs and must be reported to the Sponsor.

Events of clinical interest for this study include:

1. Potential DILI events defined as an elevated AST or ALT laboratory value that is greater than or equal to 3× the ULN and an elevated total bilirubin laboratory value that is greater than or equal to 2× the ULN and, at the same time, an alkaline phosphatase laboratory value that is less than 2× the ULN, as determined by way of protocol-specified laboratory testing or unscheduled laboratory testing.*
*Note: These criteria are based on available regulatory guidance documents. The purpose of the criteria is to specify a threshold of abnormal hepatic tests that may require an additional evaluation for an underlying etiology. The study-site guidance for assessment and follow-up of these criteria can be found in the Investigator Study File Binder (or equivalent).
2. AEC >5000 cells/μL at a single time point
3. AEC >1500 cells/μL and confirmed or suspected hypereosinophilic syndrome or eosinophil-associated organ injury; see Appendix 9 for definitions and examples.

8.4.8 Drug-device Combination Products/Combination Medicinal Products – Complaints, PQCs, and Malfunctions

The method of documenting and reporting complaints, PQCs, and malfunctions will occur as below and in Appendix 4. Refer to Appendix 7 for country-specific information and definitions.

To fulfill regulatory reporting obligations worldwide, medical device information associated with AEs will be collected and reported to the Sponsor in the same time frame as AEs per Section 8.4.1 via CRF (paper or electronic) and as per data entry guidelines.

All SAEs due to malfunction will be followed until resolution, stabilization, until the event is otherwise explained, or the participant or associated person is lost to follow-up.

PQCs/malfunctions, including those that involve a participant or any user/associated person, must be reported to the Sponsor. Sponsor shall review reported events by the investigator to fulfill the legal responsibility of notifying appropriate regulatory authorities and other entities about certain safety information relating to the drug-device combination products/combination medicinal products being used in clinical studies.

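### The SAP names no special-interest safety topic, and so plans no by-regimen count of eosinophil threshold crossings, ECIs, grouped injection-site reactions or eosinophil-driven interruptions

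*SAP*

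**What the plan says.** SAP 3.5.3.2 is one sentence: "There are no safety topics of special interest in this study".

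SAP 3.5.3.1 and Table 3 set the general safety analysis. Specific AEs or SOCs get a difference and M&N 95% CI when at least 4 participants in any group have the event. Laboratory values get summary statistics by treatment group (baseline, on treatment, change), with no between-group interval. Groups are not compared in the extension.

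The protocol says:
- Section 2.3: "The most frequently reported AEs are cutaneous AEs, including injection-site reactions, and elevated absolute eosinophil count".
- Section 4.2.1.2: "In MK-6194 studies, absolute eosinophil counts will be measured at baseline and monitored during treatment".
- Section 6.6.3: AEC above 1000 cells/µL (or a rise of at least 500 when the Screening AEC exceeds 650) triggers a repeat test. If AEC remains above 1000, "study intervention should be interrupted".
- Section 7.1: three discontinuation criteria use AEC, with cut-offs at 1500 and 5000.
- Section 8.4.7: "Selected serious and nonserious AEs are also known as ECIs and must be reported to the Sponsor". The three ECIs are potential DILI, a single AEC above 5000, and AEC above 1500 with "confirmed or suspected hypereosinophilic syndrome or eosinophil-associated organ injury; see Appendix 9 for definitions and examples".
- Section 10.3.2: an abnormal laboratory result is an AE when the investigator considers it clinically significant.

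**The concern.** Safety is one of the two primary objectives (Protocol Section 3), and the trial studies two dosing intervals. A reader will want to know how many participants on each regimen crossed the eosinophil levels at which the protocol acts. The planned tables do not answer that directly.

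An AEC between 1000 and 5000 without suspected organ injury can interrupt dosing and, if it persists at 1500 or more, end treatment. Yet it is not an ECI. It is counted by arm only if the investigator records it as an AE; otherwise it contributes only to a laboratory summary.

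The controlled window is short. After Week 24 placebo participants move to active drug (Protocol 6.3.1), so the Double-Blind Treatment Period is the only source of a placebo comparison.

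**Working it through.** **1. The SAP's own threshold reproduces.** Inputs: 55 per arm (SAP 3.8) and the M&N score method (SAP 3.5.3.1). For x events versus 0, test at zero difference: z = (x/55) / √[p(1−p)(2/55)(110/109)], with p = x/110.
- 3 versus 0: 0.0545/0.0312 = 1.75; 95% CI −1.31 to 14.91 points, includes zero.
- 4 versus 0: 0.0727/0.0359 = 2.03; 95% CI 0.45 to 17.32 points, excludes zero.

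So the SAP's reason for a cut-off of 4 is correct. The question is which events are ever counted against it.

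**2. When does an event reach 4 in one arm?** The documents give no AEC or injection-site rates, so true rates are assumed. P(X ≥ 4), X binomial with n = 55:

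| True rate | P(at least 4 of 55) |
|---|---|
| 1% | 0.2% |
| 2% | 2.4% |
| 5% | 29.6% |
| 10% | 81.3% |
| 15% | 97.4% |
| 20% | 99.8% |

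A common recorded AE gets its interval. A rare ECI almost never does and appears only as a count under its AE term.

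**3. Dependence on investigator judgement.** Suppose 8 of 55 on one regimen cross 1000 cells/µL, none exceeds 5000, none has suspected organ injury, and placebo has 0 of 55 (assumed). Counted from the laboratory data, z = 0.1455/0.0497 = 2.92. If each crossing is independently recorded as an AE with probability q, the AE table shows an interval only if at least 4 of the 8 are recorded. P(X ≥ 4), X binomial with n = 8:
- q = 0.25: 1 − (0.100 + 0.267 + 0.311 + 0.208) = 11.4%
- q = 0.50: 163/256 = 63.7%
- q = 0.75: 97.3%

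If exactly 4 are recorded, the table shows 4/55 = 7.3% where the laboratory rate is 8/55 = 14.5%.

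**4. Mean change can hide crossings.** Let all 55 start at 650 cells/µL (assumed). If 8 rise by 500, to 1150, and 47 do not change, the mean change is 8 × 500/55 = 73. If all 55 rise by 73, to 723, the mean change is the same and nobody crosses 1000. An SD or maximum may hint at the difference but does not count participants.

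**5. Grouping.** If injection-site reactions split into three terms of 3 participants each, without overlap and with none on placebo (assumed), no term reaches 4. Pooled, 9/55 versus 0/55 gives 8.8 to 28.3 points.

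**6. Feasibility.** Eosinophils are in the central laboratory panel (Protocol Table 6). Haematology is drawn from all participants at Screening and Weeks 2, 4, 8, 12, 18 and 24 (Section 1.3.1). Double-blind procedures at Week 24 precede that day's dose (Section 8.10.2). Screening AEC above 1000 is exclusionary (Section 5.2), so a later value above 1000 is a new crossing relative to the qualifying Screening result.

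**The case against.** A reader might infer that the main expected risk is not estimated by regimen at all. The documents do not support that. SAP 3.5.3.1 summarises eosinophil change by arm, and any specific AE or SOC in at least 4 participants gets a difference and interval. Injection-site reactions are AEs, so a common reaction recorded under one term is covered. Protocol 2.3 shows that raised AEC does get recorded as an AE, and a single AEC above 5000 is an ECI without any judgement step.

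A reader might also infer that potential DILI drives interruption or discontinuation. Sections 6.6 and 7.1 contain no such rule; DILI is an ECI with reporting requirements.

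An ECI is a reporting category and a special-interest topic is an analysis category, and neither document equates them. Protocol Table 5 has no special-topic row either. The eDMC reviews unblinded safety data, and the SAP calls its safety intervals descriptive. All of this stands. It makes the issue a mismatch and a reporting gap, not a formal contradiction or a lapse in participant monitoring.

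It does not close the gap. Monitoring by the eDMC does not pre-specify what the final report will show. An SOC row pools by organ system, not by this topic. The compliance formula in SAP 3.10 does not separate AEC-driven interruptions from other missed injections.

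**Conclusion.** The point holds in limited form. The statement in SAP 3.5.3.2 does not fit Protocol 2.3, 6.6.3, 7.1 and 8.4.7. The visible plan contains no by-regimen count, rate or interval for AEC at the protocol's cut-offs, and no by-regimen tabulation of ECIs, grouped injection-site reactions or AEC-driven interruptions.

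The size depends on rates that the documents do not give. For common recorded AEs the loss is small: at a true rate of 15% or more, a given arm reaches the threshold with probability of at least 97%. The loss is larger for AEC crossings below the ECI criteria, where by-arm visibility depends on how often investigators record them, and for reactions spread over several terms. The 8/55 and 9/55 examples illustrate the mechanism and are not predictions.

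Extra tables will not make rare events precise: with 0/55, the exact two-sided 95% upper bound is still 6.5%. Nor will they settle the contrast between regimens: 16/55 versus 11/55 (assumed) gives −7.2 to 25.1 points. The change is a cheap improvement to the reporting of a primary objective and leaves the efficacy conclusions untouched.

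**What to change.** Reconcile SAP 3.5.3.2 with the protocol sections above and add, for the Double-Blind Treatment Period up to the pre-dose Week 24 assessment:
- **AEC categories:** n (%) by arm with maximum post-baseline AEC >1000, ≥1500 and >5000 cells/µL, using the scheduled visits common to all participants (Weeks 2, 4, 8, 12, 18, 24). Show unscheduled, discontinuation-visit and subpopulation tests separately, because repeat tests are triggered by high values and the subpopulation is sampled more often.
- **Shift table from Screening,** which also shows rises of at least 500 in those with Screening AEC above 650.
- **Grouped injection-site reactions,** with the list of terms fixed before unblinding.
- **Intervals:** for the AEC categories and grouped reactions, the difference from placebo with M&N 95% CI for Q2W and for Q4W, where at least 4 participants in any arm have the event.
- **Counts by arm only:** ECIs (including potential DILI), and AEC-driven interruptions and discontinuations.

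Restrict the comparisons to this period, because placebo participants then switch to active drug and the SAP excludes between-group comparisons in the extension. The cut-offs serve reporting only; no clinical rule changes.

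Cost: a few more descriptive tables. The AEC tables use central laboratory data already collected. Counting AEC-driven interruptions requires the reason to be identifiable in the dosing records, which should be checked before database lock.

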### 3.5.4 Demographic and Baseline Characteristics

The number and percentage of participants randomized, completed, discontinued, and the primary reasons for discontinuation will be displayed. Demographic variables (including age, gender, race, height, weight), baseline characteristics, medical history, prior and concomitant therapies will be summarized by treatment group either by descriptive statistics or categorical tables. The comparability of the treatment group for each relevant characteristic will be assessed by the summary tables. No statistical hypothesis tests will be performed on these characteristics.

CCI

### **Safety Interim Analyses**

The eDMC will be responsible for periodic interim safety reviews. Additional details will be specified in the eDMC charter.

### **3.7 Multiplicity**

If the interim analysis for futility is conducted, an  $\alpha$ -spending of 0.0001 will be applied to the 2-sided Type I error rate of 5% for the primary hypothesis based on the Haybittle-Peto method [Haybittle, J. L. 1971] [Peto, R., et al 1976]. Multiplicity adjustment will be made for testing 2 doses on the primary endpoint for the analysis, i.e., for testing a family of the following hypotheses:

- H1(1): 3 mg MK-6194 Q4W dose is superior to placebo in the percent change from baseline in F-VASI at Week 24.
- H1(2): 3 mg MK-6194 Q2W dose is superior to placebo in the percent change from baseline in F-VASI at Week 24.

To strongly control the Type-I error rate for this family, the Hochberg procedure [Hochberg, Y. 1988] will be applied.

### 3.8 Sample Size and Power Calculations

This study will randomize 55 participants in each treatment group and has >80% power to demonstrate the superiority of at least 1 dose of MK-6194 over placebo at an overall 2-sided 0.05 PPD alpha-level, if the underlying treatment difference in percent change from baseline at Week 24 in F-VASI score is -20%. The power and sample size are based on the following assumptions: 1) a 15% drop out rate, 2) a standard deviation of 33%, pooled across treatment groups.

### 3.9 Subgroup Analyses

To assess whether the treatment effect with respect to the primary endpoint is consistent across various subgroups of the study population, the between-treatment group effect (with a nominal 95% CI) will be estimated/summarized within each subgroup of the following classification variables. For stratification factors: vitiligo status and previous JAK inhibitor use, participants will be analyzed based on the IRT values at randomization.

- Vitiligo status (active, stable)
- Baseline F-VASI (<1, ≥1)
- Gender (male, female)
- Age, years (≥18 to ≤40, >40 to ≤64, > 64)
- Race (American Indian or Alaska Native, Asian, Black or African American, Multiple, White)
- Baseline F-BSA (<1, ≥1)
- Previous JAK inhibitor use (yes, no)

To ensure a sufficient number of participants for the subgroup analysis, summary statistics including mean, SD, and 95% CI will only be provided when there are >5 participants in each subgroup level for each treatment group.

### 3.10 Compliance (Medication Adherence)

For each participant, percent compliance will then be calculated using the following formula:

$$\text{Percent Compliance} = \frac{\text{Number of Injections Received}}{\text{Number of Injections Should Have Received}} \times 100$$

Summary statistics will be provided on percent compliance by treatment group for the FAS population.

### **3.11 Extent of Exposure**

Extent of exposure will be summarized by the actual dose/intervention received. Each dose will be counted as 2 weeks of exposure.

Participants who took more than one treatment (MK-6194 and placebo) will be counted according to the time spent on each intervention.

The extent of exposure will be summarized using descriptive statistics for all participants as treated.

## 5 SUPPORTING DOCUMENTATION

### 5.1 Appendix 1: Abbreviations

Abbreviation	Expanded Term
APaT	All-Participants-as-Treated
AE	adverse event
CI	confidence interval
CGI-C	Clinical Global Impression of Change
CGI-S	Clinical Global Impression of Severity
DMC	Data Monitoring Committee
F-VASI	Facial Vitiligo Area Scoring Index
FAS	Full Analysis Set
LDA	longitudinal data analysis
MCAR	missing completely at random
MI	multiple imputation
M&N	Miettinen and Nurminen
MAR	missing at random
MNAR	missing not at random
PGIC/M	Patient Global Impression of Change/Meaningfulness
PGI-S	Patient Global Impression of Severity
T-VASI	Total Vitiligo Area Scoring Index
VitiQoL	Vitiligo-Specific Quality of Life Instrument
CCI	
VNS	Vitiligo Noticeability Scale

